Subjects will be withdrawn from the study in the event of:

1. Consent is withdrawn by the patient.
2. Patients will be withdrawn from the study if they experience intolerable or excessive side effects due to the probiotics.

Subject drop out is predicted at 10% and is taken into consideration in the sample size calculation.

7. Study Intervention

Patient will be randomized into a treatment or control group. No other treatments such as laxatives or enemas are given to all patients.

1. Treatment group.
 - a. Each patient will receive probiotics in form of granular powdered microbial cell preparation (Hexbio®) – Specialized formulation of six microbial strains containing:
 - i. Lactobacillus acidophilus BCMC® 12130
 - ii. Lactobacillus casei BCMC® 12313
 - iii. Lactobacillus lactis BCMC® 12451

- iv. Bifidobacterium bifidum BCMC® 02290
- v. Bifidobacterium infantis BCMC® 02129
- vi. Bifidobacterium longum BCMC® 02120

b. Dosage: 1 sachet twice a day after meals for 1 week.

2. Control group

- a. Each patient will receive placebo sample of similar appearance and composition but do not contain probiotics.

8. Efficacy, Safety and Other Assessments

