10.2 A written consent is obtained. (Appendix E)

10.3 The patients' demographic data and medical history will be obtained by conducting an interview and a physical examination.

10.4 In the first interview, patient will also be asked to complete a questionnaire on the gastrointestinal symptoms, stool consistency and severity of constipation.

Patients will be given 7 days' supply of placebo or probiotics, which patient are required to take each sachet of Hexbio® or placebo twice per day for 7 days.

10.5 A training of using the daily stool dairy will be done at the beginning of study. Upon completion (day 7) the dairy will be collected and data will be analyzed.

FLOW CHART

[figure not shown]

Figure 1. Flow chart of the study methodology.

GLOSSARY OF TERMS

1. Probiotics

Living microorganisms that enter the gastrointestinal tract in an active form in sufficient numbers to exert positive effect.

2. Constipation

A condition in which there is difficulty in emptying the bowels, usually associated with hardened feces.

3. Functional Constipation

A condition that fulfill the **Rome III criteria for functional constipation**.

Refer to Appendix A

4. Bristol Stool

A medical aid designed to classify the form of human feces into seven categories. Refer to Appendix B

5. Advanced Chronic Illness

An occurring when one or more conditions become serious enough that general health and functioning decline, and treatments begin to lose their impact.

6. Colony Forming Unit (CFU)

[figure not shown]
A unit used to estimate the number of viable bacteria or fungal cells in a sample.

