APPENDIX D

[figure not shown]
EVALUATING THE EFFECT OF PROBIOTICS IN CHRONIC CONSTIPATION ELDERLY PATIENTS WITH MULTIPLE CO-MORBIDITIES

QUESTIONNAIRES

[figure not shown]
Study Number:

Patient's Sticker:

[figure not shown]
1. How frequent is your bowel movements per week?

[figure not shown]
2. Do you need assistance in evacuation? (enema/digital-manual maneuvers)

[figure not shown]
3. Do you have sensation of anorectal obstruction/ blockage?

[figure not shown]
4. Feeling of incomplete evacuation?

[figure not shown]
5. Do you have lumpy or hard stools?

[figure not shown]
6. Any straining or squeezing on defecation attempts?

[figure not shown]
1. How long have you had constipation?

[figure not shown]
2. Do you have bloating in your stomach?

[figure not shown]
3. Do you have flatulence?

[figure not shown]
4. Do you have stomach cramps?

[figure not shown]
5. How many unsuccessful attempts of evacuation within 24hours?

6. Do you have abdominal pain?

7. How long do you spend in the lavatory per attempt? (minutes)

Statistical analysis Plan

The collected data was analysed using IBM SPSS Statistics for Windows version 21.0 software (IBM Corp., Armonk, NY, USA) and Microsoft Office Excel 2010software (Microsoft, Redmond, WA, USA). Statistical significance was set at $p = <0.050$.

All of the data was assessed for normality via the usual processes.

The baseline characteristic differences between the two groups were evaluated using the Mann-Whitney U and chi-squared tests. The median results of the improvement in stool frequencies and stool consistency between the treatment and placebo group were compared using the Mann-Whitney U test. The constipation-related symptom improvements were analysed using the chi-squared test.

Intention to treat analysis was used in this trial, where only the final results within the group which they were randomized, receiving the treatment and completed the treatment assignment were analysed. Participants who deviates from the protocol as being non-compliance or withdrew consent were not included into the analysis.

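### The SAP labels a completers-only, per-protocol set as intention to treat, and defines no analysis of all randomised participants

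*Combined protocol and SAP*

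**What the plan says.** The final paragraph of the Statistical analysis Plan (after Appendix D) opens with "Intention to treat analysis was used in this trial, where only the final results within the group which they were randomized, receiving the treatment" and goes on to limit the set to those "receiving the treatment and completed the treatment assignment were analysed". The next sentence reads "Participants who deviates from the protocol as being non-compliance or withdrew consent were not included into the analysis". The preceding paragraph names the comparisons this set feeds: "The median results of the improvement in stool frequencies and stool consistency" by Mann-Whitney U test, and symptom improvement by chi-squared test.

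Section 6 gives two reasons for withdrawal from the study: "Consent is withdrawn by the patient" and "Patients will be withdrawn from the study if they experience intolerable or excessive side effects due to the probiotics". On attrition it says only "Subject drop out is predicted at 10% and is taken into consideration in the sample size calculation".

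Section 10.4 describes the 7-day supply, "which patient are required to take each sachet of Hexbio® or placebo twice per day for 7 days". Sections 9.2 and 10.5 have the diary collected at day 7, on completion.

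**The concern.** Intention to treat has two parts: participants are analysed in the arm to which they were randomised, and all of them are analysed. The SAP keeps the first and drops the second. Its exclusions depend on what happens after randomisation (not completing, not complying, withdrawing consent), so the groups compared need no longer be the groups that randomisation made comparable. One route out is tied to treatment: patients withdrawn for side effects attributed to the probiotics do not complete, and so are not analysed.

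The rule governs every efficacy comparison. If anyone is excluded, a result reported as intention to treat tells readers that all randomised participants were analysed when they were not. Without exclusions by arm and reason, readers cannot judge whether the comparison is biased or towards which arm.

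The set also cannot be reproduced as written. No section says how much of the twice-daily, 7-day supply counts as compliance, so who is removed is left to judgement.

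**Working it through.** **1. Text check.** The claim rests on this and needs no calculation.

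| Element | All-randomised analysis | SAP, last paragraph |
|---|---|---|
| Grouping | Arm assigned | Arm assigned |
| Did not complete | Included | Excluded |
| Non-compliant | Included | Excluded, no threshold given |
| Withdrew consent | Included, data up to withdrawal | Excluded |

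No other section defines a full analysis set, a second analysis of all randomised participants, a missing-data rule or a sensitivity analysis. The 10% in section 6 is predicted dropout for the sample size; it does not say how dropouts are analysed, and no non-compliance rate is given.

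**2. Nothing to reproduce.** The documents state no sample size, allocation ratio, response rate or standard deviation. Everything below is illustration on assumed values.

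**3. Stool frequency, Mann-Whitney test.** Assumptions: no true effect; 50, 75 or 100 per arm; improvement = Poisson(4) after minus Poisson(2) before; two-sided 5% tie-corrected test; whole patients removed; 10,000 replicates. The simulation standard error near 5% is √(0.05 × 0.95 / 10,000) = 0.2 points. Entries are type I error (%) at 50/75/100 per arm.

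| Removed, arm A/arm B | Random from lowest third | Actual lowest | Unrelated to outcome |
|---|---|---|---|
| 15%/5% | 13.2/12.2/16.2 | 19.1/19.4/24.1 | 5.2/4.9/5.0 |
| 10%/0% | 9.6/12.9/14.1 | 14.4/20.3/22.7 | 5.1/4.7/5.2 |
| 10%/10% | 5.6/5.7/5.7 | 8.1/7.7/7.6 | not shown |

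With equal arms, 15%/5% averages (15 + 5)/2 = 10%, the documents' predicted dropout; 10%/0% averages 5%. At 50 per arm, 15% and 5% are 7.5 and 2.5 patients, so that split is only approximate.

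Raw Poisson(4) counts give nearly the same results: 15%/5% gives 12.8/12.2/16.0 (lowest third) and 18.1/17.6/24.0 (actual lowest), and no removal gives 4.5 to 5.6. In the raw-count 10%/0% case, nearly all false positives favour the arm that lost its poor responders: 8.6 of 9.1, 11.8 of 12.2 and 13.1 of 13.4 points for the lowest third.

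**4. Symptom improvement, chi-squared test.** Assume the same true improvement rate p in both arms and that every excluded participant is a non-responder. The rate among completers is then p/(1 − d), where d is the fraction excluded. For p = 0.5 and a 15%/5% split: 0.5/0.85 = 0.588 and 0.5/0.95 = 0.526, a spurious difference of 6.2 points. Over p = 0.3 to 0.6 the difference is 3.7 to 7.4 points, and the two-sided rejection rate (normal approximation, 50 to 150 per arm) is about 6.6% to 25%. Counting those exclusions as not improved restores a difference of 0.

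**5. Bound on the symptom difference.** Assume 50% improved among completers and 10% missing in each arm.
- All missing not improved: 0.9 × 0.5 = 45% in both arms, difference 0.
- Opposite outcomes by arm: 45% − (45% + 10%) = −10 points, or the reverse, +10 points.

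The width, 20 points, is the sum of the two missing fractions.

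**The case against.** The case for leaving it has four parts.

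- **Exclusions may be few and balanced.** Treatment lasts 7 days, the trial is double-blind with a placebo of similar appearance, and section 8.2 reports no adverse effects in the available trials. Nothing in the documents supports a 15%/5% or 10%/0% split, and removing the actual lowest responders is a deliberate extreme. This stands as a limit on the size. Equal removal from the lowest third gives 5.6% to 5.7%, barely above the range with nobody removed. It does not rescue the label, which is false with a single exclusion.
- **Withdrawal and exclusion are different things.** A plan may drop non-compliers from analysis without withdrawing them from the study, so the absence of non-compliance from the section 6 reasons is weak evidence. That stands. The missing compliance threshold is enough by itself to make the set irreproducible.
- **Silence on early stoppers' diaries is not a contradiction.** That is also right. It is a gap that affects how easily the fix can be carried out.
- **The SAP is in the past tense.** If the analysis is already done, a prospective redefinition is no longer available. That changes the form of the remedy, not the need for it.

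The flow chart is not shown and cannot be checked, but it could not cancel explicit SAP text.

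**Conclusion.** The concern holds with high confidence and must be fixed. The SAP's label contradicts its own definition within one paragraph, and no analysis of all randomised participants is defined. That conclusion rests on the text alone.

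The resulting bias has no derivable size or direction. It is zero if nobody is excluded, and type I error stays near 5% if exclusions are unrelated to outcome. On the assumptions shown, a 15%/5% loss of poor responders takes type I error to about 12% to 16% (random from the lowest third) or 18% to 24% (the actual lowest). These figures show the mechanism; they do not estimate this trial's error.

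**What to change.** 1. Define the primary analysis as all randomised participants in their assigned arm, regardless of compliance, deviation or completion, using all diary data recorded up to any withdrawal of consent.
2. State one rule for missing diary days, including how a participant with no post-baseline day enters. One option for stool frequency is the mean per recorded day scaled to 7 days, with zero improvement for a participant who has no post-baseline day.
3. Relabel the present set per-protocol, make it secondary, and define non-compliance for it.
4. Report exclusions by arm and reason.
5. Add a sensitivity analysis counting missing as not improved for the symptom outcomes. If a bound is wanted, assign opposite outcomes by arm, then reverse them. Apply no rank rule to stool consistency until the plan states which direction on the Bristol scale is better.

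If the analysis is already done, report the all-randomised result beside the existing one, state that it was added later, and correct the label.

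The cost is SAP wording, a little more analysis, and retrieval where possible of diaries from patients who stopped early. Where diaries cannot be recovered, the all-randomised result relies on imputation for those patients, but the corrected label, the exclusion counts and the sensitivity analysis remain feasible. The estimate may become less favourable. No extra patients are needed.

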APPENDIX B

DAILY STOOL DIARY						LIKERT SCALE / NUMERIC PAIN RATING SCALE							
Study No: _____ Patient's Sticker: _____ EVALUATING THE EFFECT OF PROBIOTICS IN CHRONIC CONSTIPATION ELDERLY PATIENTS WITH MULTIPLE CO-MORBIDITIES													
DAY	CONSTIPATION RELATED SYMPTOMS					BRISTOL STOOL CHART							
	STRAINING	PAINFUL EVACUATION	BLOATING & FLATULENCE	STOMACH CRAMPS	OTHERS		TYPE 1	TYPE 2	TYPE 3	TYPE 4	TYPE 5	TYPE 6	TYPE 7
BEFORE													
1													
2													
3													
4													
5													
6													
7													

Instructions: Please fill up the boxes according to likert scale for the constipation related symptoms and mark 'X' for the Bristol stool chart.

Bristol chart adapted from http://www.cbc.ca/stevenandchris/content/images/poop_101_1.jpg

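### The SAP excludes participants for undefined non-compliance, but no readable form or procedure records sachets taken or returned, so exclusion for missed sachets cannot be derived or audited

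*Combined protocol and SAP*

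**What the plan says.** The SAP's closing paragraph begins "Intention to treat analysis was used in this trial". The same sentence then limits the analysis to those "receiving the treatment and completed the treatment assignment were analysed", and the next one adds "Participants who deviates from the protocol as being non-compliance or withdrew consent were not included into the analysis". It gives no definition of non-compliance, no threshold, and no indication of who decides or when.

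Section 7 sets the regimen for the treatment group: "Dosage: 1 sachet twice a day after meals for 1 week". Section 10.4 applies it to both arms from a 7-day supply: "patient are required to take each sachet of Hexbio® or placebo twice per day for 7 days". On what comes back at the end, section 10.5 says "Upon completion (day 7) the dairy will be collected and data will be analyzed". The diary's own instruction (Appendix B) reads "Please fill up the boxes according to likert scale for the constipation related symptoms and mark 'X' for the Bristol stool chart".

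**The concern.** The rule decides who enters the only analysis set the SAP describes, and it acts after randomisation. To apply it to missed sachets, someone must know how many sachets each participant took. If no planned record holds that information, the exclusion rests on undocumented judgement that a later reader cannot check.

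Two things are at stake. The first is bias: a participant with a poor response or troublesome gut symptoms may be more readily classed as non-compliant, and such participants need not be equally common in the two arms. The second is interpretation: without a record of intake, a null result cannot be accompanied by any statement of how much of the scheduled product was taken.

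**Working it through.** The plan states no figure that depends on this point, so the check is a comparison of the rule with the data planned to feed it.

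**1. Scheduled dose.** Sections 7 and 10.4 agree: 2 sachets per day × 7 days = 14 sachets per participant.

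**2. Where a count could be recorded.**
- Section 8.1 (primary end point): demographic and illness data, daily stool output, consistency and symptom scores. No intake item.
- Section 9.2: participants chart stools and symptoms daily, and the diary is collected at day 7. No dosing entry.
- Sections 10.4 and 10.5: supply is handed out and the diary is collected. No return or count of sachets.
- Appendix B (diary): the labelled columns are symptoms and Bristol types, and the instruction covers only those. One column has no label in the extracted text, and the instruction gives it no dosing purpose.
- Appendix C: demographics, illnesses, baseline symptoms and previous treatment.
- Appendix D: bowel habit and symptom questions.

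The flow chart and the Appendix D figures are not shown and could not be checked. Subject to that, none of the six sources yields a number out of 14.

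**3. Whether non-compliance is defined elsewhere.** Section 6 lists two grounds for withdrawal: consent withdrawn, and intolerable or excessive side effects. Non-compliance is not among them. Withdrawal of consent is a definable event, so the gap concerns the non-compliance limb of the rule only.

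**4. What the missing threshold allows.** As a hypothetical illustration, the wording does not prevent excluding a participant who took 13 of 14 sachets (13/14 = 93%) while keeping one who took 7 of 14 (7/14 = 50%). Nothing in the planned data would reveal the inconsistency.

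**5. Timing.** Intake over the full course cannot be known before day 7, the day the outcome diary is collected. The plan does not say when the compliance decision is taken, and contains no provision that it be made without sight of the diary.

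**6. Size of the bias.** This would need the number randomised, the proportion excluded in each arm and the outcomes of those excluded. The documents give only a predicted 10% drop-out, with no sample size and no separate allowance for non-compliance. No calculation is possible.

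**The case against.** **Non-compliance need not mean missed sachets.** The protocol also bars laxatives and enemas (section 7) and requires a daily diary (section 9.2), and diary completion can be seen from the diary itself. This stands. A reader might infer that a site has nothing at all to apply the rule to, but the documents do not support that. The gap is specific to intake, although the SAP's restriction to those who completed treatment makes intake the natural reading.

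**The procedure is not described.** A reader might infer that staff must question participants at day 7 and decide once the outcome is known. No section says so. Nor is it stated that every participant self-administers: ward patients are eligible and might have drug charts, although the plan makes no use of them. What stands is the absence of a safeguard, not a demonstrated sequence.

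**The trial is double-blind with a placebo of similar appearance.** If blinding holds, nobody can exclude by knowing the arm. This is a real protection but not a full one: if the product alters bowel symptoms, or intolerance differs by arm, blinded decisions influenced by symptoms can still remove different kinds of participants from each arm.

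**Correcting the analysis set cures most of it.** True of the exclusion bias. A reader might infer that the bias persists whichever set is analysed; it does not. A treatment-policy comparison also remains readable when intake is incomplete. What persists is that dose received cannot be reported.

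**Dilution of effect.** A reader might want a percentage for how far incomplete intake shrinks the treatment difference. The documents give no intake figure and no dose-response relation. Any such percentage would restate an assumption, and it would not carry over directly to the planned Mann-Whitney and chi-squared tests. None is claimed here.

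**Conclusion.** The point holds in this form: exclusion for missed sachets shapes the analysed population but cannot be derived or audited from any data the readable plan collects, and nothing separates that decision from the diary outcome. It compounds a second problem in the same paragraph, where a set restricted to completers and compliers is labelled intention to treat.

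The direction and size of any bias are unknown and cannot be calculated from the documents. The conclusion assumes that the flow chart, the figures not shown and the unlabelled diary column hold no intake record; nothing in the surrounding text suggests they do. If all randomised participants are analysed as randomised, the exclusion bias goes. The residual point is then one of reporting: how many of the 14 sachets were taken would still be unknown when a null result is interpreted. This should be corrected; it does not by itself show that any result is wrong.

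**What to change.** 1. In the SAP, make all randomised participants, analysed in their assigned arm, the primary set. State how participants without a completed diary are handled.
2. Add two sachet-taken tick boxes to each of the day 1 to 7 rows in Appendix B.
3. Count returned sachets when the diary is collected, and log the number taken out of 14.
4. Define compliance from that count, with a threshold fixed before unblinding and applied without sight of the diary outcomes.
5. Use that definition only for a supportive analysis labelled per-protocol. Report sachets taken, and exclusions with reasons, by arm.

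The SAP is written in the past tense, so the diary change may come too late. If data are already collected, state how non-compliance was judged, report exclusions by arm with reasons, present the analysis of all randomised participants, and say plainly that intake was not measured.

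The cost is slightly more diary burden, a sachet count at diary collection (which needs the sachets to be brought back, since the plan does not say the collection is in person), and a few sentences in the SAP. No dose or treatment rule changes.
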